It is likely that the level of PEEP set after an LRM is important and this should be the minimum required to maintain PEEP-dependent re-opening of atelectatic areas while avoiding PEEP-induced lung over-inflation^{6,14,20,25,27,28}. How best to achieve this has been one of the most vexed questions in critical care^{27,28}. Various techniques have been proposed, including a) pulmonary mechanics (i.e. using super-syringe, plateau pressure etc)^{17,29,20}, b) CT guided^{27,32} and c) FiO₂/PEEP algorithms^{6,16}. However, these techniques have been criticised because they are either clinically impractical, necessitate deep sedation or paralysis, lead to large physiological perturbations, introduce dangers related to radiation exposure and patient transport, lack sound physiological rationale, or are insensitive to heterogeneous pulmonary lesions (the presence of recruitable vs non-recruitable alveoli) and may be injurious (PEEP induced over inflation)^{23,30,12,27}. Oxygen saturation measured by pulse oximetry is a familiar, simple and a physiologically sound “yard stick”, for clinicians to determine the minimum PEEP needed to maintain recruitment. In brief, the fraction of inspired oxygen (FiO₂) is adjusted to achieve a saturation of 90-92% (the “shoulder” of the oxyhaemoglobin dissociation curve), a point where even small increases in alveolar collapse (de-recruitment) will increase pulmonary shunt and reduce oxygenation as detected by a fall in saturation^{22,26}. After adequate recruitment (i.e. the SRM), PEEP is reduced in incremental steps until a drop in saturation occurs, the de-recruitment point (Fig. 3). A further LRM is then performed to re-expand these newly collapsed alveoli and the PEEP is ‘set’ at the step above the de-recruitment point (i.e. 2.5 cmH₂O higher, Fig 3). This approach has been demonstrated to lead to sustained improvements in ARDS patients^{25,31}. While Huh et al demonstrated that PEEP titration resulted in improved oxygenation levels and was safe, it did not affect mortality³². Unfortunately, this small study seemed likely to have been hindered by an inadequate LRM (max PEEP 25 cmH₂O) and a PEEP titration approach which permitted insufficient levels of PEEP (i.e. <15 cmH₂O) post LRM¹⁴.

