The mechanical ventilator settings should be Pressure Control with an inspiratory pressure of 15 ± 3 cmH₂O depending on tidal volume achieved (pre-SRM tidal volume target 4-6 ml/kg PBW). The PEEP level should be left at the level it had been immediately prior to this procedure. The FiO₂ should be adjusted (usually by turning it down) until the SaO₂ is stable between 90-92%. This may take several (often 15-30 minutes). The high pressure alarm should be set to 65 cmH₂O and the low tidal volume and minute ventilation alarms reduced to < 25% of the current settings.

Once the FiO₂ is stable (ie. no change for 3 minutes), the PEEP should be increased from the pre-randomisation baseline to 20 cmH₂O. In a stepwise fashion, this should be increased after 2 minutes to 30 cmH₂O (for 2 minutes) and then 40 cmH₂O (for 2 minutes), unless there is occurrence of (a) haemodynamic instability (defined as heart rate < 40 or > 140 bpm, ventricular tachycardia, or systolic blood pressure (SBP) < 80 mmHg), (b) marked oxygen desaturation (SaO₂ < 85%) or (c) new air leak through an intercostal catheter. The tidal volume should not be adjusted at each PEEP level, unless the tidal volume is > 6 ml/kg PBW.

The patient may cough or become restless at high PEEP levels. This may be due to expansion of collapsed lung and does not require the SRM to be discontinued. Transient reductions in tidal volume and minute ventilation are to be expected as the PEEP levels are increased. Sometimes the patient will require additional sedation.

If haemodynamic instability, marked oxygen desaturation or a new air leak occurs during the SRM, the SRM should be abandoned (with no further increases in PEEP occurring above the level where this occurred). If the

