patient is considered to be inadequately haemodynamically resuscitated for their underlying condition, then it is preferable if vasopressor or fluid resuscitation should occur over the next 30-60 minutes, and then the combined open lung procedure be resumed. If the patient is considered to be adequately haemodynamically resuscitated, then fluid loading purely for the SRM should not be undertaken. The PEEP level one level below the PEEP level at which the SRM was abandoned should be determined as the **maximum tolerated PEEP** for this specific SRM and the PEEP titration manoeuvre should now occur (i.e. if marked desaturation occurs at 40 cmH₂O the maximum tolerated PEEP should then be determined as 30 cmH₂O). The maximum tolerated PEEP for the SRM will be determined daily and may be a different value on subsequent days.

If there is no occurrence of haemodynamic instability, marked oxygen desaturation or new air leak, the PEEP should be increased to the highest level of 40 cmH₂O. This should be determined as the maximum tolerated PEEP for this SRM.

(2) PEEP titration manoeuvre

After the final SRM step has been completed (or abandoned, as above), the PEEP should be immediately reduced to 25 cmH₂O. If, however, the SRM was abandoned at 20 cm H₂O, the PEEP titration should begin at 17.5 cm H₂O. The PEEP should be left at this first setting for 3 minutes, then decreased in steps by 2.5 cmH₂O for 3 minutes at each PEEP level to a minimum of 15 cmH₂O (i.e. from 25 to 22.5 to 20 to 17.5 to 15 cmH₂O) until the **de-recruitment PEEP** is reached. If the mechanical ventilator does not have 0.5 cmH₂O increments, round the PEEP up from 22.5 to 23 and 17.5 to 18 cmH₂O. The de-recruitment PEEP is defined as the PEEP level at which the SaO₂ first decreases by $\geq 2\%$. Once the de-recruitment PEEP has been reached, there should be no further reduction in PEEP, and the brief recruitment manoeuvre should now occur.

The PEEP should not be reduced below 15 cmH₂O if desaturation does not occur. In this situation, the PEEP should be left on 15 cmH₂O and no brief recruitment manoeuvre is required (i.e. the combined open lung procedure has been completed).

(3) Brief recruitment manoeuvre

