After this de-recruitment, a 2 minute brief recruitment manoeuvre should be performed (with the inspiratory pressure set at 15 ± 3 cmH₂O) using the PEEP level that was the maximum tolerated PEEP for the recently performed SRM. After this brief recruitment manoeuvre the PEEP should be returned to the level that is 2.5 cmH₂O above the de-recruitment PEEP. If there was no desaturation to determine the de-recruitment PEEP, the PEEP should be set at 15 cmH₂O and no brief recruitment manoeuvre is required. This final PEEP level should be considered the **daily optimal PEEP** (for the subsequent period - usually 24 hours) until a subsequent combined open lung procedure is performed.

Ventilation settings immediately after the combined open lung procedure

Plateau pressure, tidal volume and pH: Once the combined open lung procedure has been completed, the pressure control level should be reduced to achieve a total pressure (i.e. inspiratory pressure + PEEP) ≤ 30 cmH₂O (preferably 25-28 cmH₂O) and a tidal volume of 4-6 ml/kg PBW. The tidal volume should be titrated down from 6 ml/kg towards 4 ml/kg if possible. The set breath rate should also be reduced aiming for a lowish pH (in the range of 7.15-7.30). The actual pH in an individual patient will depend on other factors (including level of sedation and other metabolic issues) and should be a clinical decision at the time.

[figure not shown]
The mechanical ventilator alarms should be returned to their appropriate settings.

FiO₂ and PEEP: Immediately after the combined open lung procedure, the FiO₂ should be decreased until the SaO₂ is in the target range of 90-95%. One hour after the combined open lung procedure, the SaO₂ should be noted, and recorded on the bedside PHARLAP study ventilation sheet as the subsequent **daily precise SaO₂ target** for that day.

After this 1 hour time point, a SaO₂ $\leq 2\%$ below this daily precise SaO₂ target should prompt strong consideration of re-recruitment using a brief recruitment manoeuvre (with or without an increase in FiO₂).

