Over the subsequent hours, the FiO₂ should then be decreased (if SaO₂ $> 95\%$) or increased (if SaO₂ $\leq 2\%$ below this daily precise SaO₂ target), but the PEEP should not be weaned from the daily optimal PEEP setting. The only time the PEEP may be weaned is if there is significant haemodynamic instability, a new air leak through an intercostal catheter or if the SaO₂ is above the target range ($\geq 95\%$) when the patient has been weaned to FiO₂ ≤ 0.4 . The daily optimal PEEP will be determined again the next day as part of the daily combined open lung procedure.

The minimum PEEP in the PHARLAP group is 15 cmH₂O. It should only be reduced below 15 cmH₂O once the patient meets the readiness for weaning criteria (below).

* PHARLAP ventilation at 2.5 cmH₂O PEEP higher than de-recruitment PEEP (Minimum PEEP 15 cmH₂O until weaning and P_{plat} < 30 cmH₂O) e.g. if patient has ≥2% drop in SaO₂ at 17.5 cmH₂O PEEP then PHARLAP ventilation after brief recruitment manoeuvre at 20 cmH₂O PEEP

Neuromuscular blocking drugs: Neuromuscular blocking drugs should be used as judged appropriate by the treating clinician and their current unit policies.

Ongoing mechanical ventilation in the PHARLAP group

Goals: The goals of mechanical ventilation should always remain as follows:

- Tidal volume: 4-6 ml/kg PBW
- Breath rate: ≤ 35 breaths/minute
- Total pressure (ie. inspiratory pressure + PEEP): ≤ 30 cmH₂O (ideal range 25-28 cmH₂O)
- SaO₂ 90-95% (if a PaO₂ is available, the aim for this is 60-80 mmHg). Within this range, re-recruitment using a brief recruitment manoeuvre is encouraged for reductions in SaO₂ of ≥ 2% below the daily precise SaO₂ target.

Permissive hypercapnia: The approach should be as follows:

- The tidal volume should be continued to be titrated downwards to achieve a tidal volume 4-6 ml/kg PBW and a plateau pressure < 30 cmH₂O (ideal range 25-28 cmH₂O). The set breath rate should also be reduced aiming for a lowish pH (in the range of 7.15-7.30).
- Hypercapnia and acidosis should be tolerated if pH ≥ 7.15.
- If pH < 7.15, the breath rate should be increased in steps of 4 to a maximum of 35 breaths/minute.
- If pH remains < 7.15 (after above), tidal volume should be increased by 1 ml/kg PBW at a time (but to a maximum total pressure [ie. inspiratory pressure + PEEP] of 35 cmH₂O).

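### After a staircase abandoned at 30 cmH2O, the brief manoeuvre runs at PEEP 20, which is at or below the de-recruitment PEEP if saturation falls at 20 or higher

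*Combined protocol and SAP*

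**What the plan says.** The rules are in the protocol under *The combined open lung procedure in the PHARLAP group*. The staircase raises PEEP to 20, 30 and 40 cmH2O. If it is stopped early, "The PEEP level one level below the PEEP level at which the SRM was abandoned should be determined as" the maximum tolerated PEEP for that staircase; the protocol's example is 40 giving 30.

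For the titration step, the text covers a staircase that is completed "or abandoned, as above), the PEEP should be immediately reduced to 25" cmH2O. The one exception begins "If, however, the SRM was abandoned at 20" cmH2O, and there titration starts at 17.5. PEEP then goes down in steps of 2.5 to a floor of 15, stopping when saturation first falls by 2% or more.

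The brief manoeuvre follows, "using the PEEP level that was the maximum tolerated PEEP for the recently performed SRM". The next instruction is "After this brief recruitment manoeuvre the PEEP should be returned to the level that is 2.5" cmH2O above the de-recruitment PEEP. The Background section on untitrated PEEP gives the purpose: "A further LRM is then performed to re-expand these newly collapsed alveoli". Inspiratory pressure is 15 ± 3 cmH2O, in the staircase "depending on tidal volume achieved".

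For later desaturations, *Ongoing recruitment manoeuvres in the PHARLAP group* tells staff to increase PEEP to the maximum tolerated level for 2 minutes. They then return to the daily optimal PEEP, or to 2.5 above it if there was no clear precipitant. Set PEEP may not exceed 25.

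**The concern.** The text adjusts the start of titration for abandonment at 20 but not for abandonment at 30. In that case titration begins 5 cmH2O above the level later used to re-recruit. If the lung de-recruits early in the descent, the step meant to re-open it applies no more PEEP than the level at which it closed.

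The effect lasts for the day. Combined procedures and separate staircases are barred outside the daily session, so the brief manoeuvre is the only re-recruitment tool until the next one. The list of reasons to omit it does not include a maximum tolerated PEEP at or below the current setting. *Management of severe hypoxaemia in the PHARLAP group* considers rescue therapy when a brief manoeuvre has failed, or when one of the listed criteria rules it out. In this branch no listed criterion need apply. What is at stake is an intervention rule that fails at its own purpose, and sites improvising differently when they meet it.

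**Working it through.** **Inputs**, all from the sections named above: staircase levels 20, 30, 40; titration levels 25, 22.5, 20, 17.5, 15; set-PEEP limit 25.

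**The protocol's own examples first.** Abandoned at 40: one level down is 30, as stated. De-recruitment at 17.5: 17.5 + 2.5 = 20, as in the note to the procedure figure. Both reproduce.

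**Abandoned at 30.** Maximum tolerated PEEP (MTP) = 20, one level below 30. This value is not printed; it follows from the rule and the 40-to-30 example. Titration starts at 25. With DR the de-recruitment PEEP:

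- brief manoeuvre relative to collapse = MTP − DR
- set PEEP = the smaller of DR + 2.5 and 25
- first later manoeuvre = MTP − set PEEP

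| DR | MTP − DR | Set PEEP | MTP − set PEEP |
|---|---|---|---|
| 25 | −5 | 25 (27.5 before the limit) | −5 |
| 22.5 | −2.5 | 25 | −5 |
| 20 | 0 | 22.5 | −2.5 |
| 17.5 | +2.5 | 20 | 0 |
| 15 | +5 | 17.5 | +2.5 |
| none | no manoeuvre needed | 15 | +5 |

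The in-procedure conflict occurs in 3 of 6 branches. These are branches of a rule and carry no probabilities.

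**Other paths.** Abandoned at 40, MTP = 30: MTP − DR runs from +5 to +15. Completed staircase, MTP = 40: +15 to +25. Neither conflicts. Abandonment at 20 is outside this point, because there is no staircase step below it from which to take a figure.

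**Total pressure within the procedure.** Let inspiratory pressure lie anywhere from 12 to 18 at each step. The lowest difference is (20 + 12) − (DR + 18) and the highest is (20 + 18) − (DR + 12):

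- DR 25: −11 to +1
- DR 22.5: −8.5 to +3.5
- DR 20: −6 to +6

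With inspiratory pressure unchanged, the differences are −5, −2.5 and 0. The claim is therefore made on PEEP only.

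**Duration of later manoeuvres.** At most 4 × 2 = 8 minutes per 24 hours.

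**The case against.** A reader might infer that the protocol orders staff to drop PEEP in a patient who has just desaturated, against its own rule "but the PEEP should not be weaned from the daily optimal PEEP setting". The text does not go that far. The later instruction is to increase PEEP; from 22.5 or 25 an increase to 20 is impossible, which makes the instruction inapplicable rather than a clear order to decrease. Two minutes followed by immediate return is also not plainly weaning, which in context describes ongoing titration.

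Nor does lower PEEP establish lower distending pressure. After the procedure, total pressure is held at 30 or less, preferably 25–28. The later instruction gives no inspiratory pressure. If 15 ± 3 carries over (an assumption), a manoeuvre at PEEP 20 reaches 32–38, which is at least 2 above that ceiling. The exception is the low-pH allowance of up to 35.

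The branch is also narrowed by existing rules. In a patient judged under-resuscitated, resuscitation and resumption of the procedure are preferred. The contraindications already bar manoeuvres during an active air leak through an intercostal catheter, ventricular tachycardia, or mean pressure below 60 mmHg despite support. Capping the manoeuvre at a tolerated level is a defensible safety choice, and FiO2 increases, rescue therapy and the next day's titration remain.

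All of this limits the consequences but leaves the in-procedure conflict standing. Marked desaturation, for example, is a reason to abandon the staircase but is not a listed contraindication.

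**Conclusion.** The point holds in limited form. It applies to a patient whose staircase is abandoned at 30, who proceeds to titration and who has no persisting contraindication. If saturation falls at 25, 22.5 or 20, the brief manoeuvre is 5 below, 2.5 below or at the de-recruitment PEEP and, on PEEP, cannot do its stated job. Later that day the instruction to increase PEEP to 20 cannot be followed as worded; a literal 20 would mean 5, 5 or 2.5 cmH2O less PEEP for 2 minutes.

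The conclusion rests on reading the level below 30 as 20 and on the written text alone, since the procedure figure was not visible. Frequency is unknown, total pressure is undetermined and no clinical harm is shown. The wording should be corrected because the correction is cheap.

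**What to change.** Under *(3) Brief recruitment manoeuvre*, state that it is performed only if the maximum tolerated PEEP exceeds the de-recruitment PEEP. Otherwise go directly to de-recruitment PEEP + 2.5, up to the limit of 25.

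Under *Ongoing recruitment manoeuvres*, state that PEEP is never lowered for a brief manoeuvre. If the maximum tolerated PEEP is below the current set PEEP, omit the manoeuvre and raise FiO2 as needed. For desaturation with no clear precipitant, keep the existing 2.5 step up to 25; a patient set at 22.5 would still go to 25. The test should be below, not at or below, so that de-recruitment at 17.5 with PEEP set at 20 is not drawn in at the first later manoeuvre.

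State that severe hypoxaemia in this branch may go to rescue therapy under the provision for a manoeuvre that is not indicated. Make the procedure figure and bedside sheet match. Leave the start of titration to the investigators: starting at 17.5 would remove the conflict but could not detect collapse at 20 to 25.

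The cost is a short amendment reported to ethics committees and a site notice. The sample size does not change. The downside is that these patients get no brief manoeuvre, and rescue therapy may be considered slightly earlier in this branch. That would occur in the PHARLAP arm only, and rescue therapy use is a secondary outcome, so the amendment should say so.

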- The expiratory pause should be removed, and 30 seconds waited, before a 0.5 second inspiratory pause should be set to measure plateau pressure.
- Within the same breath, expired tidal volume and plateau pressure should be measured.
- Static respiratory compliance should be calculated as tidal volume / (plateau pressure – total PEEP).

Collection of specimens at baseline:

Patients in both groups should have specimens of blood and bronchoalveolar lavage (BAL) fluid collected prior to commencement of the assigned mechanical ventilation strategy.

The blood specimen should be collected from the arterial line and sent with the BAL specimen to the site's pathology department for appropriate spinning and storage. These will be sent in batches to Flinders Medical Centre for measurement of IL-6 and IL-8 levels in both blood and BAL.

To perform the BAL, we recommend using a bronchoscopic method. Alternatively a non-bronchoscopic technique using the KimVent BAL Cath (Bronchial Aspirate Sampling Catheter) can also be used. There are two sizes of KimVent BAL Caths – 13F is recommended for a size 7cm ETT and smaller and 16F is recommended for a size 7.5cm ETT and larger. These will be provided to all sites by the ANZIC-RC. Whichever method is used, at least 10 ml of BAL fluid should be collected. A right-sided BAL is preferred for consistent sampling.

Appendix 2 includes instructions on how to collect the specimen if a bronchoscopic method is used. It also includes instructions on how to perform the non-bronchoscopic technique using the KimVent BAL Cath to collect the BAL specimen.

If the patient has been assigned to the PHARLAP group, this procedure should now be followed as soon as possible (but no later than 4 hours after randomisation) by a combined open lung procedure (see below). Satisfactory haemodynamic resuscitation may also be required before 4 hours after randomisation.

If it is not feasible to collect a BAL sample because of limited resources to perform the bronchoscopy or the Investigator is unfamiliar with the use of the KimVent BAL cath or it may cause undue delay in recruitment then

a BAL sample is not required to be collected once enrolled. We understand that this may occur from time to time. However, every attempt should be made to collect the blood sample on all patients.

Control group mechanical ventilation

Initial commencement of mechanical ventilation in the control group

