Neither the combined open lung procedure nor independently performed SRMs should be performed at times other than this daily morning intervention.

The **lack of improvement in static lung compliance** definition will be met if the static lung compliance after the staircase recruitment manoeuvre on day 3 is lower than the static lung compliance assessed prior to the performance of the initial (day 1) combined open lung procedure. Any patient who meets this criterion will have no further combined open lung procedures or brief recruitment manoeuvres and should have the PEEP set on 15 cmH₂O (or higher if clinically appropriate) unless the patient meets the readiness for weaning criteria.

No combined open lung procedures or brief recruitment manoeuvres should be performed after day 5. If the patient has not met readiness for weaning criteria, the optimal PEEP should be set at 15 cmH₂O (or higher if clinically appropriate) unless the patient meets the readiness for weaning criteria.

Desaturation: We recommend patients receive a chest x-ray for significant persistent desaturation to rule out barotrauma before a brief recruitment manoeuvre or further combined open lung procedures are performed.

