- The PEEP should be increased to the maximum tolerated PEEP determined during the most recently performed SRM, left at that level for 2 minutes, and then immediately returned to the daily optimal PEEP determined by that same SRM.

If an oxygen desaturation ($\geq 2\%$ below the daily precise SaO₂ target) occurs with no clear precipitating event (ie. potentially a deterioration in lung function), the brief recruitment manoeuvre should be performed as follows:

- The PEEP should be increased to the maximum tolerated PEEP determined during the most recently performed SRM, left at that level for 2 minutes, and then immediately returned to 2.5 cmH₂O (rounded up by 0.5 if the ventilator does not use 0.5 cmH₂O settings) higher than the previous daily optimal PEEP set during that SRM.
- This new PEEP level should be considered the new daily optimal PEEP level for the subsequent part of that day until the next SRM is performed. The FiO₂ should then be decreased as required to maintain the SaO₂ aim.
- The PEEP should not be set higher than 25 cmH₂O at any time during the study (with the exception of the staircase recruitment manoeuvre).

Brief recruitment manoeuvres should not be repeated more frequently than 2 hourly and not more than a maximum of 4 manoeuvres per 24 hours.

Ventilation during patient transfers: Mechanical ventilation should continue to adhere to this PHARLAP group strategy during patient transfers (to diagnostic or therapeutic procedures outside the ICU) where possible. However if the patient receives mechanical ventilation using either a manual (hand-bagging) circuit or a transport ventilator that is not practically able to deliver the PHARLAP group mechanical ventilation settings, patients may be ventilated using alternative means whilst away from the ICU. Resumption of PHARLAP group mechanical ventilation (including performance of a brief recruitment manoeuvre if indicated)

should occur as soon as possible after the transfer. A brief recruitment manoeuvre will usually be required (see above on this page).

Specific measurements on Day 3 in the PHARLAP group

Patients in both groups should have 2 things measured on day 3:

1. Static respiratory compliance should be measured (see page 22 for technique).
2. Specimens of blood and BAL should be collected (see below) – **after** static respiratory compliance has been measured. The BAL should be collected using the same technique as was used at baseline.

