Independent senior statisticians at Monash University will perform data analysis. Baseline and outcome variables will be compared using Chi-square tests for categorical variables, Student's t-test for normally distributed continuous variables and Wilcoxon rank-sum tests for non-normally distributed continuous variables. Duration of ventilation will be analysed using Cox-Proportional Hazards regression with deceased patients censored at death, allowing for results to be reported using Kaplan Meier curves. Furthermore, duration of ventilation will be stratified into survivors and non-survivors. If as expected, the duration of ventilation in each strata is well approximated by a log-normal distribution, this will enable log-transformed duration of ventilation to be analysed using parametric analysis (student t-tests) and reported as a ratio (95%CI). If normality cannot be achieved then the data would subsequently be analysed non-parametrically. Should any baseline imbalances be found to exist between groups, additional sensitivity analysis will be performed using Cox Proportional Hazards regression adjusting for imbalanced covariates. All analyses will be intention-to-treat. A complete statistical analysis plan will be finalised prior to study completion.

Interim analysis

One midpoint interim analysis (after primary outcome data is available for 170 patients) will be performed to assess accumulated safety data. This will be reported to the Data Safety Monitoring Committee, but will not be made available to the Management Committee or to study sites.

Subgroup analyses

We plan to compare study outcomes in the following pre-specified subgroups:

- (a) Patients with severe ARDS ($\text{PaO}_2/\text{FiO}_2 < 100$) versus patients with moderate ARDS ($\text{PaO}_2/\text{FiO}_2$ 100-200 mmHg) at enrolment.
- (b) Patients with diffuse ARDS versus patients with focal ARDS at enrolment (determined by independent radiologists).
- (c) Patients who are responders to the open lung strategy versus patients who are non-responders (defined as meeting lack of improvement in static lung compliance definition).

SAFETY OF SUBJECTS

Data Safety Monitoring Committee

An independent Data Safety Monitoring Committee, comprising experts in clinical trials, biostatistics and intensive care will be established. The committee will be responsible for monitoring mortality related to serious adverse events, serious adverse events and reviewing the interim safety analysis.

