- Baseline to day 3 change in IL-8 and IL-6 concentrations in non-bronchoscopic broncho-alveolar lavage
- Baseline to day 3 change in IL-8 and IL-6 concentrations in plasma

In addition we will also study the ARDS subgroups (based on CXR) on basis of response to recruitment (in the PHARLAP study group): i.e. recruitment manoeuvre responders - defined as patients who improve static lung compliance with recruitment manoeuvre (i.e. > 0 ml/cmH₂O) from baseline to day 2 and non-responders (Patients who do not improve static lung compliance) as patients with diffuse ARDS can be hypothesised to have more response with recruitment.

Study design

This will be a sub-study of all patients who are enrolled into the PHARLAP study. Informed consent is obtained for all patients enrolled in the PHARLAP study, the participant information and consent form includes details of the diffuse versus focal substudy.

[figure not shown]
Methods

A chest radiograph at the time of ARDS onset (as determined by the study coordinator at the study site) will be de-identified, given a unique study number and saved to the PHARLAP database available for qualitative analysis post-hoc. Each patient will also have blood and BAL sample collected at baseline and day 3.

At the completion of the study the patients will be divided into predefined subgroups – focal, patchy and diffuse ARDS by independent radiologists. Additional data required for this sub study is the ventilator settings at the time of each CXR (PEEP, tidal volume, peak airway pressure and plateau pressure and respiratory rate) and blood gases.

Once patient’s subgroups are identified (focal, patchy and diffuse) we will compare the subgroups of ARDS managed by intervention or control strategy with markers of lung injury (plasma and BAL IL8 and IL6 levels) and patient related outcomes such as ventilator free days and other clinical/patient centred efficacy outcomes (Primary and secondary outcomes of PHARLAP) (see study flow chart below).

Study Flow chart

Statistical considerations

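### Subgroup (c) and the Appendix 7 responder analysis keep only the sign of a noisy compliance change, and their two definitions conflict on day and on ties; the measured change should be analysed as continuous

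*Combined protocol and SAP*

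**What the plan says.** The section on ongoing recruitment manoeuvres in the PHARLAP group contains a lack-of-improvement criterion. This "definition will be met if the static lung compliance after the staircase recruitment manoeuvre on day 3 is lower than the static lung compliance" measured before the first (day 1) combined open lung procedure. The cut-off is therefore a change of exactly zero, and an unchanged value does not meet the criterion. The criterion also steers treatment: "Any patient who meets this criterion will have no further combined open lung procedures or brief recruitment manoeuvres".

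Under Statistical considerations, Subgroup analyses, item (c) makes the same criterion an analysis split: "Patients who are responders to the open lung strategy versus patients who are non-responders (defined as meeting lack of improvement" in static compliance.

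The section on measuring static respiratory compliance says: "Within the same breath, expired tidal volume and plateau pressure should be measured". It continues: "Static respiratory compliance should be calculated as tidal volume / (plateau pressure – total PEEP"). No repeat, averaging, minimum change or error allowance appears anywhere in the documents. The day 3 section for the PHARLAP group adds: "Static respiratory compliance should be measured (see page 22 for technique"). That reading is requested in both arms and is not tied to the day-3 staircase manoeuvre.

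Appendix 7 (Study outcome measures) has its own responder definition for the PHARLAP arm: "defined as patients who improve static lung compliance with recruitment manoeuvre (i.e. > 0" ml/cmH2O), from baseline to day 2. The schedule of events in Appendix 3 lists static compliance on days 1 and 3 only.

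**The concern.** Two things look wrong.

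First, a zero cut-off on the difference between two single-breath readings gives the same label to a patient whose compliance rose by 0.1 as to one whose compliance rose by 15. It also lets reading error decide the label for anyone near zero. Misclassification weakens any real link between recruitability and outcome. Reducing a continuous change to its sign discards information that the trial has already collected.

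Second, the trial would report responders under two definitions that differ in the day, in the handling of ties, and possibly in whether the reading follows a staircase manoeuvre. One of them relies on a day-2 measurement that is not scheduled. A null or inconsistent result from the two analyses would be hard to interpret.

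**Working it through.** **Plan's own figure.** There is none to reproduce. The documents state no responder rate and no measurement error for compliance.

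**Inputs from the documents**
- Cut-off of zero change (protocol criterion and Appendix 7).
- One breath per reading (compliance measurement section).
- Typical compliance of 30 ml/cmH2O, the patchy value in Appendix 7, Table 1. The ± values in that table describe spread between patients, not reading error.
- 340 patients. With 1:1 allocation (assumed; the ratio is not stated) the PHARLAP arm has about 170.

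**Assumed inputs**
- Coefficient of variation (CV) of one reading: 5%, 10% or 15%, with independent errors.
- For the population figures: true compliance N(30, 8) and true change N(2, 5) ml/cmH2O.

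**Is the CV range plausible?** Take an illustrative tidal volume of 420 ml and pressure difference of 14 cmH2O: 420/14 = 30.0. A 1 cmH2O reading error gives 420/15 = 28.0 or 420/13 = 32.3, a shift of about 7–8% and enough to change a label near zero.

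**No true change.** With equally distributed errors, P(day 3 ≥ baseline) = 0.5 + P(tie)/2. This is 50% before ties, whatever the CV (49.9–50.1% in simulation).

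**Fixed true change Δ from C = 30.** P(labelled responder) = Φ(Δ / (CV × √(C² + (C+Δ)²))).
- Δ = +2: √(900 + 1024) = 43.9. At CV 5%, 2/2.19 = 0.91 and Φ = 0.82, so 18% are called non-responders. At 10% and 15% the figures are 32% and 38%.
- Δ = −2: √(900 + 784) = 41.0. At CV 5%, −2/2.05 = −0.97 and Φ = 0.16, so 16% are called responders. At 10% and 15% the figures are 31% and 37%.

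**Mixed population, true change N(2, 5), by simulation**

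| CV | Labelled responder | Misclassified | Median absolute true change in the misclassified | Labelled non-responders who truly improved | Information kept by the sign |
|---|---|---|---|---|---|
| 5% | 64% | 12% | 1.0 | 19% | 61% |
| 10% | 61% | 21% | 1.8 | 33% | 64% |
| 15% | 58% | 28% | 2.2–2.3 | 42% | 67% |

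Information kept is the squared correlation of the sign with an outcome linear in true change, divided by the same quantity for the measured change. If all 170 PHARLAP patients had the reading, 12–28% would be about 20–47 patients.

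**The two definitions side by side**

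| | Protocol criterion, used in subgroup (c) | Appendix 7 |
|---|---|---|
| Follow-up reading | Day 3, after the staircase manoeuvre | Day 2 |
| Unchanged value | Response | Non-response |
| Scheduled in Appendix 3? | Day 3 yes, but its timing relative to the staircase manoeuvre is not given | No day-2 compliance |

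The difference in days matters even without ties. If nothing truly changes and all three readings have the same error distribution, the two labels disagree when the shared baseline is the middle of the three values, which has probability 1/3.

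**The case against.** The strongest reply is that 50% is a property of any zero cut-off under no change and symmetric error, and not a prediction. This stands. The pilot reported better compliance with PHARLAP (Background, pilot trial), and the scenario above labels 58–64% as responders. The baseline reading is taken at pre-randomisation settings and the criterion's day-3 reading after a staircase manoeuvre, with no common PEEP stated. A systematic shift could therefore move the share either way.

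A reader might also infer that the subgroup is sorted largely by noise. The figures do not support that: 72–88% are classified correctly in the same scenario, and the errors cluster near zero change. The measurement instructions also limit error by requiring no spontaneous breaths, set pauses, and volume and pressure from one breath. The CV range comes from no document.

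A third tempting inference is that the rate of tied readings measures how often the two definitions disagree. It does not. They use different days, so a day-3 tie does not fix the day-2 sign, and the documents do not state rounding to whole units. A common tie rule alone would not reconcile them.

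Finally, a continuous analysis does not cure the subgroup's larger limits. Response is observed after randomisation. Controls never have a staircase manoeuvre (severe hypoxaemia section, control group). Patients labelled non-responders stop the procedures. This also stands, and it shapes the fix.

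**Conclusion.** The point holds in a limited form. Both responder analyses replace a measured change by its sign without allowing for reading error, and their definitions conflict on day and on ties. The conflict is plain from the text and needs no assumption.

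The size of the first part depends on the assumed 5–15% CV and N(2, 5) true change: about 12–28% misclassified, and about 61–67% of the information kept. The coin-toss result applies only to patients with no true change. All of this concerns only PHARLAP patients who have the day-3 reading.

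The consequence is modest. One of three subgroups and a substudy that describes itself as hypothesis-generating are affected; the primary analysis is not. This is an improvement to consider while the full SAP is still to be finalised. It is no criticism of the criterion's bedside use.

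**What to change.** In the SAP:

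1. In subgroup (c) and the Appendix 7 responder analysis, use the measured baseline-to-day-3 change in static compliance as a continuous variable.
2. Restrict both analyses to the PHARLAP arm and label them exploratory, because the variable arises after randomisation and controls have no staircase manoeuvre.
3. State which day-3 reading is used: the one after the staircase manoeuvre, as in the protocol criterion, or the scheduled day-3 measurement.
4. Reconcile day 2 in Appendix 7 with the protocol criterion and the schedule of events.
5. Keep the sign rule only to describe who met the protocol criterion.

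The bedside use of that criterion is outside this point and stays with the investigators. The cost is SAP wording and a little more analysis work; no new measurement is needed.
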